6.2.2 Reportable Adverse Events

Related and unrelated ocular adverse events will be reported only in the study eye as there is no plausible reason to believe that the DMEK procedure could affect a non-study eye. Since the DEKS does not involve investigational drugs or devices and participants in this study would have undergone DMEK regardless of study participation, related adverse events are those limited to events that are related or possibly related to randomization of donor tissue or study procedures of blood sample collection and specular microscopy. Eye banks will follow their standard procedures for reporting of AEs related to the donor cornea as required to the FDA and the EBAA.

6.2.2.1 Events Requiring Expedited Reporting

The following events will require expedited reporting to the CC (see 6.3).

- Endophthalmitis
- Microbial keratitis (bacterial, fungal, parasitic) within 3 months of DMEK

6.2.2.2 Other Adverse Events

All deaths will be reported, with cause of death if known; other systemic events will not be reported unless determined to be related to study participation.

The following events will be reported on a separate online AE form:

[figure not shown]
- non-serious events related to study procedure of blood sample collection that requires some form of medical intervention (*note: expected events such as pain, bruising, irritation at site of fingerstick do not require reporting*)
- non-serious events related to study procedure of specular microscopy that requires medical intervention

The following ocular adverse events of interest, even if serious, will be reported on electronic study visit case report forms and not on separate AE Forms:

- Surgical complications
- Dislocated donor
- Donor detachment
- Clouded recipient corneal stroma
- Wound leak
- Donor wrinkles/folds/curls
- Anterior chamber abnormalities
- New onset glaucoma
- Graft rejection
- Other serious ocular abnormalities (ex. trauma, retinal detachment, suprachoroidal hemorrhage)

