Endpoint	
Primary Efficacy Outcome: Graft failure within 1 year of surgery
 
Key Secondary Efficacy Outcomes: Change in central endothelial cell density (ECD) at 1 year after surgery
 
Key Safety Outcomes: Endophthalmitis, microbial keratitis (bacterial, fungal, parasitic) within 3 months of DMEK, and other unexpected ocular serious adverse events (SAEs).
 
Other Key Analyses: Develop separate models for predicting 1) risk of graft failure and 2) ECL based on severity of diabetes in the donor as measured by eye bank-determined diabetes risk categorization scores, post-mortem HbA1c, and skin advanced glycation endproducts (AGE) and oxidation markers.

Population	
Participant Inclusion Criteria:
 
 1) Age range 30- < 91 years with minimum life expectancy of at least 1 year 2) Willingness to return to study site for follow up at 1 month and 1 year 3) Fluent in English or Spanish 4) Willingness to have fingerstick blood sample collected to determine HbA1c level at entry and at 1 year. The participant must agree to have their primary care provider contacted (or an appropriate referral provided) if they were not known to have diabetes and the HbA1c suggests they may have diabetes. Similarly, if already known to have diabetes and the HbA1c is high, the participant must agree to have their primary care provider contacted or an appropriate referral provided. 
Study Eye Eligibility Criteria
 
Inclusion:
 
 1. At least one eye clinically recommended for DMEK that is able to be scheduled for DMEK between 5 to 90 days after enrollment 2. If second eye is enrolled, must be scheduled for DMEK between 7 days and 6 months after DMEK on the first eye. 3. Presence of a condition related to endothelial dysfunction which will be treated by DMEK 
 • Eligible indications for DMEK include: 
 a. Presence of Fuchs endothelial corneal dystrophy (FECD) meeting at least one of the following:

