6.2.3 Relationship of Adverse Event to Study Procedure

The study investigator will assess the relationship of any adverse event requiring reporting on an AE form to be related or unrelated by determining if there is a reasonable possibility that the adverse event may have been caused by a study procedure (in the DEKS study procedures include randomization of donor tissue by donor diabetes status, blood sample collection and specular microscopy).

To ensure consistency of adverse event causality assessments, investigators should apply the following general guideline when determining whether an adverse event is related:

Yes

There is a plausible temporal relationship between the onset of the adverse event and the study procedure, and the adverse event cannot be readily explained by the participant's clinical state, intercurrent illness, or concomitant therapies; and/or the adverse event follows a known pattern of response to the study procedure; and/or the adverse event abates or resolves upon discontinuation of the study procedure and, if applicable, reappears upon re-challenge.

No

Evidence exists that the adverse event has an etiology other than the study procedure (e.g., preexisting medical condition, underlying disease, concurrent illness, or concomitant medication); and/or the adverse event has no plausible temporal relationship to study device, drug or procedure.

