6.3 Timing of Event Reporting

The events noted in 6.2.2.1 and any SAEs possibly related to study participation must be reported to the CC within 24 hours of the site becoming aware of the event. This can occur via phone or email, or by completion of the online serious adverse event form. If the form is not initially completed, it should be completed as soon as possible after there is sufficient information to evaluate the event. The site will be responsible for reporting the event to the JCHR IRB within 7 days.

All other reportable AEs (as defined in 6.2.2.2) should be submitted by completion on the online form within 7 days of the site becoming aware of the event.

The CC will notify all participating investigators of any adverse event that is serious, related, and unexpected. Notification will be made within 10 working days after the CC becomes aware of the event.

Each principal investigator is responsible for reporting serious study-related adverse events to the JCHR IRB as the overseeing IRB. Sites must report all serious, related adverse events within seven calendar days to the IRB.

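### Sections 6.2.2.2 and 6.3 conflict on serious ocular events, leaving most of them no stated path to the 24-hour report or to the unexpected ocular SAE outcome

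*Combined protocol and SAP*

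**What the plan says.** All references are to the combined protocol and SAP.

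- **Routing (6.2.2.2).** A list of "ocular adverse events of interest, even if serious, will be reported on electronic study visit case report forms and not on separate AE Forms". It includes dislocated donor, donor detachment and graft rejection, and closes with "Other serious ocular abnormalities (ex. trauma, retinal detachment, suprachoroidal hemorrhage").
- **Expedited events (6.2.2.1).** Endophthalmitis, and microbial keratitis within 3 months of DMEK. Neither is on the visit-form list.
- **24-hour rule (6.3).** Besides those two infections, "any SAEs possibly related to study participation must be reported to the CC within 24 hours of the site becoming aware of the event". On the channel: "This can occur via phone or email, or by completion of the online serious adverse event form". And then: "If the form is not initially completed, it should be completed as soon as possible".
- **Meaning of related (6.2.2).** Limited to events related or possibly related to the randomization of donor tissue, blood sampling or specular microscopy.
- **Relatedness (6.2.3).** The investigator will "assess the relationship of any adverse event requiring reporting on an AE form".
- **Expectedness (6.2.5).** The Medical Monitor classifies it for SAEs considered possibly related to a study procedure.
- **Key safety outcomes (Protocol Summary, Endpoint).** The two infections, "and other unexpected ocular serious adverse events (SAEs").
- **Visit forms (4.3.1).** One at 1 month and one at 12 months, each looking back over standard-of-care visits. Graft failure or regraft has its own form, completed when it happens.

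**The concern.** The 24-hour report starts from a judgement that a serious event is possibly related. For listed ocular events, the plan places that judgement on a form that 6.2.2.2 tells the site not to complete. Several later steps depend on the same judgement: expectedness in 6.2.5, and, in 6.3, the site's 7-day report to the IRB and the CC's notice to investigators of serious, related and unexpected events.

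Tissue assignment is the trial's intervention, and some listed events could plausibly reflect it. Section 1.1 cites more graft dislocation with diabetic donors in the earlier preservation-time trial, and dislocation and detachment are both on the list.

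Two things are at stake: whether the Medical Monitor and DSMC see a possibly tissue-related ocular SAE promptly, and whether one component of the key safety outcome has a definition that can be applied to the data.

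**Working it through.** **Step 1. Follow events through the text.**

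| Event | Route | Relatedness judged? | Expectedness judged? | Reaches the CC |
|---|---|---|---|---|
| Endophthalmitis; microbial keratitis within 3 months | Expedited (6.2.2.1) | Not needed for the 24-hour report | If considered possibly related | Within 24 hours |
| Graft failure or regraft | Graft failure form (4.3.1; Table 1, footnote 3) | Not stated | Not stated | When it occurs |
| Donor dislocation or detachment, early and serious | Visit form (6.2.2.2) | Not stated | Not stated | 1-month form |
| Any other serious ocular event after the 1-month visit | Visit form, by the catch-all | Not stated | Not stated | 12-month form |

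Rows 3 and 4 hold the conflict. If the investigator thinks such an event is possibly related to the assigned tissue, 6.3 calls for notice within 24 hours and an SAE form, while 6.2.2.2 rules out a separate AE form. If the investigator follows 6.2.2.2 alone, no text asks the relatedness question.

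**Step 2. The outcome.** To count as an unexpected ocular SAE, an event needs an expectedness classification. Section 6.2.5 provides one only for SAEs considered possibly related, and 6.2.3 prescribes that consideration only for AE-form events. Section 8.8 tabulates complications and abnormalities on ocular examination by donor group, so the events can be counted. No section says which of them are unexpected.

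**Step 3. The delay.** Inputs from Table 2: 1-month visit at Day 30, window ±10; 12-month visit at Day 364, window −30/+100.

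- Close of the 12-month window: 364 + 100 = Day 464, which matches the limit in 8.8.
- Gap between visit forms at target: 364 − 30 = 334 days.
- Shortest gap within windows: (364 − 30) − (30 + 10) = 334 − 40 = 294 days.
- Longest gap within windows: 464 − (30 − 10) = 464 − 20 = 444 days.

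These are the waits for an event just after the 1-month visit that is recorded only on the next visit form; a later event waits less. DSMC safety review is semi-annual (8.11). Taking half a year as 182 days, 294/182 = 1.6, 334/182 = 1.8 and 444/182 = 2.4. At least one review would pass in the first two cases and at least two in the last.

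**The case against.** The strongest reply is that 6.2.2.2 only says which form holds the data, while 6.3 separately says how fast related SAEs must be notified, by phone or email if need be. Other routes exist too. Section 6.1 requires prompt reporting of unanticipated problems, with no AE form involved. Section 6.4 has the Medical Monitor review all reported adverse events. Under 6.2.2, eye banks report tissue-related events through their own channels. DMEK is standard care, and surgeons are masked to donor diabetes, so a case-level opinion on tissue relatedness carries limited information; the between-group rates in 8.8 carry more.

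Much of this stands. A reader might infer that the 24-hour rule cannot work at all. The documents do not support that: it works for the two infections, and its phone and email channel does not depend on a visit form. A reader might also infer that serious ocular events are recorded only at 1 and 12 months. That ignores the graft failure form. Nor does the long delay apply to the dislocation example, since positioning and attachment are recorded from surgery to the 1-month visit (Table 1). The dislocation signal itself came from a trial of a different procedure, DSAEK. Section 8.5 considers suprachoroidal hemorrhage highly unlikely to be related to donor diabetes.

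The reply does not remove the conflict. Phone and email are means of sending a report; they do not supply the relatedness judgement, and 6.3 still wants the form afterwards. Section 6.1 covers only events that are unexpected, at least possibly related, and suggestive of greater risk than was known, which is narrower than a related SAE. The Medical Monitor can review only what has been reported. Masking weakens the relatedness judgement, but the plan's own expedited rule rests on it.

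One reservation matters. A figure in 6.2.2.2, at the head of the list of events that go on an AE form, and the flow chart in 6.2.2.3 are not visible in the extracted text. The bullets that remain cover only non-serious events. A missing line could send related SAEs to an AE form and resolve part of the conflict. Even so, the visit-form instruction would still apply to serious events, and the order of precedence would need stating.

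**Conclusion.** The point holds as a conflict between sections and a gap in a definition. For listed ocular events that are serious, the visible text bars a separate AE form in one place and calls for an SAE form in another whenever the event is possibly related. Apart from endophthalmitis and early microbial keratitis, it gives ocular SAEs no stated path to the judgements on which the 24-hour report and the unexpected ocular SAE outcome depend.

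The timing problem is limited to ocular SAEs after the 1-month visit other than the expedited infections, graft failure and regraft. For an event just after that visit, the wait is 334 days at target and 294 to 444 days within windows.

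It would go too far to infer that these events are lost or cannot be tabulated. Section 8.8 keeps the counts by donor group; what is missing is timeliness and the related and unexpected classifications. The primary endpoint is not affected. The conclusion assumes that sites follow 6.2.2.2 literally and that the unseen figure and flow chart do not settle the matter.

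**What to change.** First check the original page of 6.2.2.2 and the flow chart in 6.2.2.3. Then reconcile 6.2.2.2 with 6.2.3, 6.2.5 and 6.3:

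1. State that a listed ocular event also goes on the online SAE form, when the site learns of it, if it is serious and possibly related to the assigned tissue or study procedures, or serious and unexpected.
2. Have relatedness and expectedness recorded for each such event, and extend 6.2.3 and 6.2.5 to cover them.
3. State that the unexpected ocular SAE outcome is derived from those records.
4. Keep the visit-form route for all other listed events.

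The cost is a short amendment and a small number of extra forms. No visits or procedures are added.

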6.2.2.3 Clinical Site AE Reporting Flow Chart

The following flow chart outlines the required AE reporting procedures described above:

6.2.3 Relationship of Adverse Event to Study Procedure

The study investigator will assess the relationship of any adverse event requiring reporting on an AE form to be related or unrelated by determining if there is a reasonable possibility that the adverse event may have been caused by a study procedure (in the DEKS study procedures include randomization of donor tissue by donor diabetes status, blood sample collection and specular microscopy).

To ensure consistency of adverse event causality assessments, investigators should apply the following general guideline when determining whether an adverse event is related:

Yes

There is a plausible temporal relationship between the onset of the adverse event and the study procedure, and the adverse event cannot be readily explained by the participant's clinical state, intercurrent illness, or concomitant therapies; and/or the adverse event follows a known pattern of response to the study procedure; and/or the adverse event abates or resolves upon discontinuation of the study procedure and, if applicable, reappears upon re-challenge.

No

Evidence exists that the adverse event has an etiology other than the study procedure (e.g., preexisting medical condition, underlying disease, concurrent illness, or concomitant medication); and/or the adverse event has no plausible temporal relationship to study device, drug or procedure.

6.2.4 Severity (Intensity) of Adverse Events

The severity (intensity) of an adverse event requiring reporting on an AE form will be rated on a three-point scale: (1) mild, (2) moderate, or (3) severe. A severity assessment is a clinical determination of the intensity of an event. Thus, a severe adverse event is not necessarily serious. For example, itching for several days may be rated as severe, but may not be clinically serious.

- **MILD:** Usually transient, requires no special treatment, and does not interfere with the participant's daily activities.
- **MODERATE:** Usually causes a low level of inconvenience, discomfort or concern to the participant and may interfere with daily activities, but is usually ameliorated by simple therapeutic measures and participant is able to continue in study.
- **SEVERE:** Interrupts a participant's usual daily activities, causes severe discomfort, may cause discontinuation of study device, and generally requires systemic drug therapy or other treatment.

6.2.5 Expectedness

For a serious adverse event that is considered possibly related to a study procedure as noted in 6.2.1, the Medical Monitor will classify the event as unexpected if the nature, severity, or frequency of the event is not consistent with the risk information.

6.2.6 Coding of Adverse Events

Each AE form is reviewed by the Medical Monitor to assess safety and to verify the coding and the reporting that is required.

Adverse events will be coded using the MedDRA dictionary. To facilitate coding, the site will enter a preliminary MedDRA code that describes the type of event, which the Medical Monitor may accept or change (the Medical Monitor's MedDRA coding will be used for all reporting). The Medical Monitor will review the investigator's assessment of causality and may agree or disagree. Both the investigator's and Medical Monitor's assessments will be recorded. The Medical Monitor will have the final say in determining the causality as well as whether an event is classified as a serious adverse event.

6.2.7 Outcome of Adverse Events

The outcome of each reportable adverse event (requiring completion of an AE form) will be classified by the investigator as follows:

- **RECOVERED/RESOLVED (COMPLETE RECOVERY)** – The participant recovered from the AE/SAE without sequelae. Record the AE/SAE stop date.
- **RECOVERED/RESOLVED WITH SEQUELAE** – AE/SAE where the subject recuperated but retained pathological conditions resulting from the prior disease or injury. Record the AE/SAE stop date.
- **FATAL** – A fatal outcome is defined as the SAE that resulted in death. Only the event that was the cause of death should be reported as fatal. AEs/SAEs that were ongoing at the time of death; however, were not the cause of death, will be recorded as "resolved" at the time of death.

- **ONGOING NOT RECOVERED/NOT RESOLVED** – An ongoing AE/SAE is defined as an ongoing event with an undetermined outcome.
 - ◆ An ongoing outcome will require follow-up by the site in order to determine the final outcome of the AE/SAE.
 - ◆ The outcome of an ongoing event at the time of death that was not the cause of death, will be updated and recorded as “resolved” with the date of death recorded as the stop date.
- **ONGOING (MEDICALLY STABLE)** – AE/SAE is ongoing, but medically stable. For example, a chronic condition where no further change is expected.

If any reportable adverse events are ongoing when a participant completes the study (or withdraws), data collection will continue until the specific adverse event is resolved.

Note: participants should continue to receive appropriate medical care for all adverse events after their participation in the study ends, even if they are not reportable adverse events.

6.3 Timing of Event Reporting

The events noted in 6.2.2.1 and any SAEs possibly related to study participation must be reported to the CC within 24 hours of the site becoming aware of the event. This can occur via phone or email, or by completion of the online serious adverse event form. If the form is not initially completed, it should be completed as soon as possible after there is sufficient information to evaluate the event. The site will be responsible for reporting the event to the JCHR IRB within 7 days.

All other reportable AEs (as defined in 6.2.2.2) should be submitted by completion on the online form within 7 days of the site becoming aware of the event.

The CC will notify all participating investigators of any adverse event that is serious, related, and unexpected. Notification will be made within 10 working days after the CC becomes aware of the event.

Each principal investigator is responsible for reporting serious study-related adverse events to the JCHR IRB as the overseeing IRB. Sites must report all serious, related adverse events within seven calendar days to the IRB.

6.4 Safety Oversight

The study Medical Monitor will review all adverse events that are reported during the study. Additionally, the Medical Monitor will review compiled safety data at periodic intervals (generally timed to the review of compiled safety data by the DSMC).

The DSMC will review compiled safety data at periodic intervals. The DSMC can recommend modifications to the study protocol or suspension or outright stoppage of the study if deemed necessary based on the totality of safety data available. Details regarding DSMC review will be documented in a separate DSMC document.

Chapter 7: Miscellaneous Considerations

7.1 Pregnancy Reporting

If pregnancy occurs, the participant will remain in the study since the study intervention will have been completed and remaining in the study consists of only low risk follow-up procedures. The occurrence of pregnancy will be reported to the CC.

7.2 Participant Compensation

Participant compensation will be specified in the informed consent form.

7.3 Participant Withdrawal

Participation in the study is voluntary, and a participant may withdraw at any time. For participants who withdraw, their data will be used up until the time of withdrawal.

7.4 Confidentiality

For security and confidentiality purposes, both the donor and the human subject participants will be assigned identifiers that will be used instead of their names for study purposes. However, protected health information, such as name and social security number, will need to be shared with the specific eye bank processing the participant's donor tissue (eye banks require additional unique patient identifiers) as part of the EBAA standard requirements of transplant processing and notification; this information will be shared directly between the clinical site and their respective eye bank as per standard practices and therefore will not be stored in the study database. Alternatively, participant name and contact information will be shared by the sites through the study database and will be accessible (limited access) to members in the CWRU Coordinating Center for purposes of contacting participants that may be lost to follow-up. De-identified or coded participant information may also be provided to research sites involved in the study. The samples sent to the laboratories will be coded for HbA1c and AGE testing, and the labs will not receive any identifying information other than date of collection. Similarly, the images sent to CIARC will be coded and are not identifiable other than date of collection.

Chapter 8: Statistical Considerations

